##### **Secondary objectives**

- 1) To assess overall and progression-free survival distributions (Arms 1, 2 & 3).
- 2) To assess the objective response rate to treatment (Arms 1, 2 & 3).
- 3) To further delineate the safety profile of the combination of everolimus and TMZ (Arm 2)
- 4) To assess whether treatment (Arms 1, 2 & 3) provides clinical benefit by reducing seizure frequency

##### **Exploratory objectives**

- 1) Pending adequate funding, to assess the ability of metabolic and physiologic imaging parameters such as MR spectroscopy, perfusion-weighted imaging, and diffusion-weighted imaging to predict clinically relevant endpoints such as time to progression and survival.
- 2) To assess for an association between the presence/absence of clonal or subclonal genetic mutations in the PI3K pathway and Median PFS, Objective Response Rate (ORR), *PTEN* methylation, and the immunohistochemical measurements of the PI3K pathway activation in patients treated with everolimus or TMZ and everolimus.
- 3) To longitudinally assess quality of life (QoL) in low-grade glioma patients over the course of treatment with everolimus (Arms 1 & 3).

#### Endpoints:

##### **Primary Endpoint:**

CC# 131012  
Phase 2 – Everolimus with/without TMZ  
Version 6.0  
Version Date: 20Feb2018

---

[figure not shown]
Arms 1 & 2: progression-free survival at 33 months (PFS-33)  
Arm 3: progression-free survival at 38 months (PFS-38)

**Secondary Endpoints (for all arms):**

- 1) Median and distribution of overall survival (OS) and PFS
- 2) Objective Response Rate (ORR)
- 3) Number of adverse events related to combination treatment
- 4) Rate of Reduction in Seizures (as outlined in van den Bent, Wefel *et al.* 2011)

#### **4 Study design**

Treatment for patients with previously untreated LGG will be selected by whether or not their tumor has ATRX loss and/or 1p/19q chromosomal co-deletion. If the tumor is ATRX lost or 1p/19q intact, then patients will be further selected by whether or not their tumor demonstrates activation of the PI3K/mTOR pathway. If activation is present, patients will be treated in Arm 1 with single-agent everolimus at 10 mg daily continuously. If activation is not present, patients will be treated in Arm 2 with combined everolimus and TMZ. Everolimus will be given at 10 mg daily continuously, and TMZ will be dosed initially at 150 mg/m^2/day for 5 days out of a 28-day cycle. If ATRX is intact, 1p/19q co-deletion should be confirmed, or if only 1p/19q co-deletion is available and present, patients will be treated in Arm 3 with single-agent everolimus at 10 mg daily continuously. In all arms, treatment with everolimus will continue for up to 24 cycles, after which patients will be followed with interval MRIs until progression. In Arm 2, TMZ will be stopped after 12 cycles.

**Figure 2-1: Study Schema**

## 5 Population

The total number of patients enrolled in this study will be 105, with 35 patients in each of the three treatment arms.

### 5.1 Inclusion and Exclusion criteria

Patients must have baseline evaluations performed prior to the first dose of study drug and must meet all inclusion and exclusion criteria. Results of all baseline evaluations, which assure that all inclusion and exclusion criteria have been satisfied, must be reviewed by the Principal Investigator or his/her designee prior to enrollment of that patient. In addition, the patient must be thoroughly informed about all aspects of the study, including the study visit schedule and required evaluations and all regulatory requirements for informed consent. The written informed consent must be obtained from the patient prior to enrollment. The following criteria apply to all patients enrolled onto the study unless otherwise specified.

#### Inclusion criteria:

1. Age  $\geq$  18 years
2. KPS  $\geq$  60
3. Adequate bone marrow function as shown by: ANC  $\geq$  1.5  $\times$  10^9/L, Platelets  $\geq$  100  $\times$  10^9/L, Hb  $\geq$  9.0 g/dL;
4. Adequate liver function as shown by:
  - a. Total serum bilirubin  $\leq$  2.0 mg/dL,

- b. ALT and AST  $\leq$  2.5x ULN,
- c. INR  $\leq$  2;
- 5. Adequate renal function: serum creatinine  $\leq$  1.5 x ULN;
- 6. Fasting serum cholesterol  $\leq$  300 mg/dL OR  $\leq$  7.75 mmol/L AND fasting triglycerides  $\leq$  2.5x ULN. NOTE: In case one or both of these thresholds are exceeded, the patient can only be included after initiation of appropriate lipid lowering medication with confirmed reduction of lab values to within eligibility parameters;
- 7. Signed informed consent obtained prior to any screening procedures.
- 8. Patients must have histologically proven supratentorial low-grade glioma at initial diagnosis and at the time of any subsequent surgeries; pathology must have been reviewed by UCSF neuropathology. Eligible low-grade gliomas include: astrocytoma, oligodendrogloma and mixed oligoastrocytoma. Pilocytic astrocytomas are excluded.
- 9. Patient's tumor must have documentation of the presence of an IDH-1 and/or IDH-2 mutation of any type.
- 10. Results of ATRX and/or 1p/19q chromosomal status: if ATRX is lost, 1p/19q status is not required. If ATRX is intact, 1p/19q chromosomal status must be available to permit treatment selection.
- 11. Results of pRAS40 testing.
- 12. Patients must have evaluable disease. Patients must begin treatment within 120 days of most recent surgical procedure.

**Exclusion criteria:**

- 1. Patients may not have had any prior tumor treatment except for surgery, and must have adequately recovered from surgery.
- 2. Known intolerance or hypersensitivity to everolimus or other rapamycin analogs (e.g. sirolimus, temsirolimus) or to temozolomide;
- 3. Known impairment of gastrointestinal (GI) function or GI disease that may significantly alter the absorption of oral everolimus or temozolomide;
- 4. Uncontrolled diabetes mellitus as defined by HbA1c  $>$  8.0% despite adequate therapy. Patients with a known history of impaired fasting glucose or diabetes mellitus (DM) may be included, however blood glucose and antidiabetic treatment must be monitored closely throughout the trial and adjusted as necessary;
- 5. Patients who have any severe and/or uncontrolled medical conditions such as:
  - a. unstable angina pectoris, symptomatic congestive heart failure, myocardial infarction  $\leq$  6 months prior to start of everolimus, serious uncontrolled cardiac arrhythmia, or any other clinically significant cardiac disease
  - b. symptomatic congestive heart failure of New York heart Association Class III or IV
  - c. active (acute or chronic) or uncontrolled severe infection, liver disease such as cirrhosis, decompensated liver disease, and chronic hepatitis (i.e. quantifiable HBV-DNA and/or positive HbsAg, quantifiable HCV-RNA),
  - d. known severely impaired lung function (spirometry and DLCO 50% or less of normal and O2 saturation 88% or less at rest on room air),

---

- e. active, bleeding diathesis;
- 6. Chronic treatment with corticosteroids or other immunosuppressive agents. Topical or inhaled corticosteroids are allowed, and treatment with low dose Decadron ( $\leq 3$ mg daily) is allowed;
- 7. Known history of HIV seropositivity;
- 8. Positive serological test results for hepatitis B (see Section 5.2, Table 5)
- 9. Positive serological test result for hepatitis C (see Section 5.2)
- 10. Patients who have received live attenuated vaccines within 1 week of start of treatment and during the study. Patient should also avoid close contact with others who have received live attenuated vaccines. Examples of live attenuated vaccines include intranasal influenza, measles, mumps, rubella, oral polio, BCG, yellow fever, varicella and TY21a typhoid vaccines;
- 11. Patients who have a history of another primary malignancy, with the exceptions of: non-melanoma skin cancer, and carcinoma in situ of the cervix, uterus, or breast, unless the patient has been disease free for  $\geq 3$  years;
- 12. Patients with a history of non-compliance to medical regimens or who are considered potentially unreliable or will not be able to complete the entire study;
- 13. Patients who are currently part of or have participated in any clinical investigation with an investigational therapeutic drug within 1 month prior to dosing;
- 14. Pregnant or nursing (lactating) women;
- 15. Women of child-bearing potential (WOCBP), defined as all women physiologically capable of becoming pregnant, who are not willing to use adequate methods of contraception during the study and for 8 weeks after the end of treatment.  
Women are considered post-menopausal and not of child-bearing potential if they have had 12 months of natural (spontaneous) amenorrhea with an appropriate clinical profile (e.g. age appropriate, history of vasomotor symptoms) or have had surgical bilateral oophorectomy (with or without hysterectomy) or tubal ligation at least six weeks prior to randomization. In the case of oophorectomy alone, only when the reproductive status of the woman has been confirmed by follow up hormone level assessment is she considered not of child-bearing potential.
- 16. Male patients whose sexual partner(s) are WOCBP who are not willing to use adequate contraception, during the study and for 8 weeks after the end of treatment

## 5.2 Screening for hepatitis B and C

Prior to start of everolimus, patients should be tested for hepatitis B serologic markers, that is, HBsAg, HBs Ab, and HBC Ab. Patients should also be tested for hepatitis C using HCVAb.

**Table 5-1 Action to be taken based on screening hepatitis B results**

Test	Result	Result	Result	Result
HBsAg	+	-	-	-
HBsAb	+ or -	+ and no prior HBV vaccination	+ or -	- or + with prior HBV vaccination
HBcAb	+ or -	+ or -	+	-
Recommendation	Patient is not eligible for study			Patient is eligible for study

## 6 Treatment

### 6.1 Study treatment

#### 6.1.1 Everolimus

Everolimus is supplied by Novartis. See Section 1.2.1 for additional drug information. Everolimus is formulated as tablets for oral administration, of 2.5mg, 5mg, and 10mg strength. Tablets are blister-packed under aluminum foil, which should be opened only at the time of administration as drug is both hygroscopic and light-sensitive.

Medication labels will comply with US legal requirements and be printed in English. They will supply no information about the patient. The storage conditions for everolimus will be described on the medication label.

All dosages prescribed and dispensed to the patient and all dose changes during the study must be recorded.

#### 6.1.2 Temozolomide

Temozolomide for this trial will be obtained from commercial suppliers. Formulation and packaging may vary depending on the commercial suppliers; there will be no study-specific labeling unless required by local regulations.

Please refer to the package insert for information regarding the preparation and dispensing of temozolomide (see Appendix 4).

#### 6.1.3 Treatment assignment

Patient treatment will be selected by whether or not their tumor tissue demonstrates 1p/19q chromosomal co-deletion and by PI3K/mTOR pathway activation (see Section 7.3.2). As per Section 4, patients whose tumors are ATRX lost and/or 1p/19q intact and that demonstrate pathway activation will be treated on Arm 1 with single-agent everolimus. Patients whose tumors are ATRX lost and/or 1p/19q intact but do not demonstrate pathway activation will be treated on Arm 2 with the combination of everolimus and temozolomide. Patients whose tumors are 1p/19q co-deleted will be treated on Arm 3 with single-agent everolimus regardless of mTOR pathway status. Patients whose tumors are ATRX intact must be tested for 1p/19q

---

co-deletion and, if co-deletion is confirmed they will be treated on Arm 3 with single-agent everolimus regardless of mTOR pathway status.

#### **6.1.4 Everolimus dosing regimen**

The investigator should promote compliance by instructing the patient to take the study drug exactly as prescribed and by stating that compliance is necessary for the patient's safety and the validity of the study. The patient should be instructed to contact the investigator if he/she is unable for any reason to take the study drug as prescribed.

Everolimus should be administered orally once daily at the same time every day, either consistently with or consistently without food. The initial dose will be 10 mg daily. The tablets should be swallowed whole with a glass of water and should not be chewed or crushed. For patients unable to swallow tablets, the tablet(s) should be dispersed completely in a glass of water (containing approximately 30 mL) by gently stirring, immediately prior to drinking. The glass should be rinsed with the same volume of water and the rinse completely swallowed to ensure the entire dose is administered.

If vomiting occurs, no attempt should be made to replace the vomited dose. Patients should be instructed that if they miss a dose on one day, they must not take any extra dose the next day, but instead to immediately contact the study center as soon as possible to ask for advice.

#### **6.1.5 Temozolomide dosing regimen**

Temozolomide will be orally self-administered at approximately the same time each day on days 1 through 5 of each 28 day dosing cycle. A temozolomide dose of 150 mg/m^2 per day will be given for Cycle 1 of TMZ. This dose may increase to 200 mg/m^2 body surface area per day in subsequent TMZ cycles per the treating physician's discretion. Any change in weight of more than 10% will require re-calculation of the administered temozolomide dose; otherwise, dosing may be based on the baseline weight. The total dose of TMZ shall be rounded to the nearest 5 mg. Dosing should occur according to instructions in the product label and per standard clinical practice.

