## 2.4 Safety of combined everolimus and temozolomide

The combination of everolimus and temozolomide has been reported in a phase I study (Mason, Macneil, et al., 2012) combining the two drugs for treatment of GBM, either in the adjuvant setting immediately after radiation or in the setting of first recurrence after initial treatment, as well as in a phase II study in patients with metastatic, unresectable melanoma (Dronca, Allred, et al, 2013). In the phase I study, the recommended phase II dose was everolimus 10 mg/day with TMZ 150 mg/m^2/d x 5 days out of 28. At this dose, myelosuppression was mild, with 2 patients each having grade 3 thrombocytopenia, lymphopenia, and granulocytopenia. Common adverse events otherwise included mild fatigue, flushing, pruritus, rash, mucositis, nausea and vomiting, headache, cough and mild pneumonitis. The combination of everolimus and TMZ at 200 mg/m^2/d was attempted only in combination with an everolimus dose of 2.5 mg/day; this dose level had no DLTs, but 3 of 4 patients required a delay in restarting TMZ, and 2 of 3 patients were dose-reduced to TMZ 150 mg/m^2/d, so no further attempts to treat patients at 200 mg/m^2/d were made in that study. In the phase II study in melanoma patients, patients were treated with everolimus 10 mg/d 5 days/week, with TMZ dosed at 200 mg/m^2/d x 5 days out of 28. 9 out of 48 patients required dose reduction due to myelotoxicity, but overall the combination was well-tolerated, with the most common other toxicities being fatigue, nausea and elevated liver enzymes.

Given this clinical experience with the combination of everolimus and TMZ, we will treat patients at 10 mg daily of everolimus and 150 mg/m^2/d x 5 days out of 28 for the first cycle. If the first cycle is well-tolerated, the treating physician will have the option to increase TMZ to 200 mg/m^2/d for the second cycle and beyond.

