**Table 6-7 Temozolomide Dose-Adjustment Criteria for Hematologic Toxicity**

Nadir Toxicity Level	Nadir ANC/ $\mu\text{L}$	Nadir Platelets/ $\mu\text{L}$	Temodar Modification
1	1500–1999	75–99, 999	Dose unchanged from previous
2	1000–1499	50–74, 999	Dose unchanged from previous
3	500–999	25–49, 999	Decrease dose to next lower dose level
4	<500	<25,000	Decrease dose to next lower dose level

---

Note: Dose levels (daily dose): 200 mg/m^2/day, 150 mg/m^2/day, 100 mg/m^2/day.

**Non-Hematological Criteria:** Subsequent courses will start (as long as the treatment is beneficial) after complete resolution of toxicities to grade 2 or less. A minimum 2-week rest period will be required if there is grade 3 or greater non-hematological toxicity, and dosages for the subsequent course will be one dose level below the dose that produced toxicity of grade 3 or greater, except doses will not be reduced for grade 3 nausea/emasis unless it is grade 3 despite optimal medical management.

If the patient experiences grade 3 or greater hematological or non-hematological toxicity after 2 dose reductions of temozolomide, he or she will discontinue temozolomide for the remainder of the study. Patients may continue to be treated with everolimus.

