### 7.1.2 Assessments During Treatment

- A cycle will be 28 days in length regardless of treatment delays; in particular, for patients also receiving temozolomide, if there is a delay in re-initiating temozolomide, Day 1 of that cycle will not shift with the temozolomide.
- At the end of cycle 1 (Day 28, +/- 7 days), a toxicity check will be performed via telephone call.

- Clinical Evaluation: Clinical assessments will be required every 2 cycles for the first 12 cycles, then every 3 cycles for the next 12 cycles. Whenever possible, all assessments at each scheduled time-point will be completed in a single clinic visit. Clinical assessments performed at required visits will include the following:
  - Karnofsky performance status (Appendix 1)
  - Neurologic Examination (see below)
  - Physical Examination
  - Pulse Oximetry measurements
  - Vital Signs: pulse, blood pressure, respiration rate, temperature and weight.
  - A Neuro Exam Score should be recorded at each patient visit according to the following scale (compared to baseline, defined as neurologic exam at time of screening).

+2	Definitely better
+1	Possibly better
0	Unchanged
-1	Possibly worse
-2	Definitely worse
- Radiographic Evaluation: An MRI will be required every 2 cycles for 12 cycles, and every 3 months for the subsequent 12 cycles. MR spectroscopy scans are optional, and will be done at the following timepoints: baseline, at the end of cycles 2 and 6, and at the time of tumor progression.
  - Imaging Score: This will be recorded every time a patient has an imaging study.

+3	Disappearance of tumor (CR)
+2	Definitely better (PR)
+1	Possibly better
0	Unchanged
-1	Possibly worse
-2	Definitely worse (PD)
-3	Development of a new lesion (PD)
- Laboratory Evaluation:
  - **Arms 1 and 3** (everolimus alone):
    - CBC, platelets, differential (Day 28 (+/- 7 days) of each cycle)

- **Arm 2** (everolimus and temozolomide)
  - CBC, platelets, differential (Days 21 (+/- 3 days) and 28 (+/- 3 days) after the first dose of temozolomide while on temozolomide and everolimus, then Day 28 (+/- 7 days) when on everolimus alone.)
- **All Arms:**
  - Sodium, potassium, chloride, bicarbonate, calcium, fasting glucose, albumin, total protein, BUN, serum creatinine (Day 28 (+/- 7 days) of each cycle)
  - T. Bilirubin, AST, ALT, alkaline phosphatase, phosphorus (Day 28 (+/- 7 days) of each cycle)

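### The rules for raising temozolomide from 150 to 200 mg/m² in Arm 2 do not agree, and they give different doses after a level 1 or 2 nadir

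*Combined protocol and SAP*

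**What the plan says.** Four places bear on the dose of temozolomide after cycle 1.

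- **Section 2.4:** "If the first cycle is well-tolerated, the treating physician will have the option to increase TMZ to 200" mg/m² per day, from the second cycle on. What counts as well tolerated is not defined.
- **Section 6.1.5:** cycle 1 is given at 150 mg/m² per day, and then "This dose may increase to 200 mg/m 2 body surface area per day in subsequent TMZ cycles", at the physician's discretion. No tolerance condition is attached. The section ends by referring dosing generally to the product label and standard practice.
- **Table 6-1b:** 200 mg/m² is dose level +1, reached at cycle 2 at the physician's discretion.
- **Section 6.2.3 and Table 6-7:** the dose of later cycles is set by the ANC and platelet nadirs of the cycle just before. At nadir levels 1 and 2 the instruction is "Dose unchanged from previous"; at levels 3 and 4 the dose goes down one level.

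Section 6.2.3 also delays a course until ANC is at least 1500/µL, platelets are at least 100,000/µL, and drug-associated non-hematological toxicity is at grade 2 or below, or at baseline, and poses no hazard in the investigator's view.

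On timing, Section 7.1.2 says: "At the end of cycle 1 (Day 28, +/- 7 days), a toxicity check will be performed via telephone call". Chemistry and liver tests have the same 7-day window. The Arm 2 blood counts are at Days 21 and 28, each within 3 days.

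**The concern.** Two operative rules can be applied to the same patient on the same day and return different temozolomide doses, and no passage says which prevails. One lets the physician raise the dose; the other fixes it from the nadir. The condition that might settle the matter, a well-tolerated first cycle, appears only in the rationale and not in the dosing section or the dose table.

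The dose given to such a patient would then depend on which passage the treating physician follows. Further describing the safety of the combination is a stated secondary objective for Arm 2, and a clear description needs a dose rule that can be stated once. PFS-33 in Arm 2 is estimated in the same patients, although the documents give no basis for sizing any effect on it.

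**Working it through.** The plan gives no figure on this point to reproduce. The check is a comparison of the passages, with some dose and calendar arithmetic.

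**1. The rules side by side**

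| Place | Condition | When | Can the dose rise? |
|---|---|---|---|
| Section 2.4 | First cycle well tolerated (undefined) | Cycle 2 and later | Yes, physician's option |
| Section 6.1.5 | None beyond discretion | Any later cycle | Yes |
| Table 6-1b | None beyond discretion | Cycle 2 | Yes |
| Section 6.2.3 with Table 6-7 | Previous cycle's nadir | Every later cycle | No: hold or reduce |

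**2. One patient through each rule**

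Take a cycle 1 nadir ANC of 1200/µL with platelets never below 100,000/µL, and ANC back to 1500/µL by Day 28. The nadir lies in 1000–1499, so it is level 2. The recovery criteria are met, assuming no other toxicity.

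- Table 6-7: 150 mg/m².
- Section 6.1.5: 150 or 200, at discretion.
- Table 6-1b: 150 or 200 at cycle 2, at discretion.
- Section 2.4: 150 or 200 if the cycle counts as well tolerated, otherwise 150. The text does not say whether a level 2 nadir counts.

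The same split arises anywhere in levels 1 and 2 (ANC 1000–1999/µL or platelets 50,000–99,999/µL, with neither count lower). With no nadir in the table's range, Table 6-7 has no row and is silent, so there is no direct clash. At levels 3 and 4 it orders a reduction. An increase there would need general discretion to override a direct instruction, and I do not count it.

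**3. Size of the difference per course**

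At 150: 150 × 5 = 750 mg/m². At 200: 200 × 5 = 1000 mg/m². The ratio is 1000/750 = 1.33, or one third more.

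**4. Calendar**

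Count Day 1 as the first temozolomide dose, with 28-day cycles and no delay. Cycle 2 temozolomide then falls on Days 29–33.

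| Assessment | Window | Allowed days | On or after Day 29 | After Day 33 |
|---|---|---|---|---|
| Telephone check | 28 ± 7 = Days 21–35 | 15 | 7 | 2 |
| Chemistry and liver tests | 28 ± 7 = Days 21–35 | 15 | 7 | 2 |
| Second blood count | 28 ± 3 = Days 25–31 | 7 | 3 | 0 |
| First blood count | 21 ± 3 = Days 18–24 | 7 | 0 | 0 |

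The first count always precedes cycle 2. The other three may be done on schedule and still come after the first cycle 2 dose. Clinic assessments are every two cycles, so none is required between cycles 1 and 2.

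**The case against.** **The passages can be read together.** Sections 2.4 and 6.1.5 and Table 6-1b all leave the decision to the physician. The latter two are silent on tolerance; they do not contradict it. Everyone starts at 150 and the note under Table 6-7 lists 200 as a level, so that table presupposes that some patients are raised. A coherent reading exists: no nadir toxicity leaves the option open, levels 1 and 2 hold the dose, levels 3 and 4 reduce it. This stands as a possible reading and confines the dose conflict to levels 1 and 2. It is not what the text says, however: Section 6.2.3 is unqualified, and Section 6.1.5 makes no exception for those nadirs.

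**The timing is mostly handled.** A reader might infer from the windows that a raised dose can be given with no knowledge of cycle 1 toxicity. The documents do not support that. The recovery criteria cannot be applied without counts and a toxicity judgement before the next course, and the Day 21 count always comes first. What remains is that those criteria decide whether to re-treat and not whether to raise the dose, that they accept non-hematological toxicity up to grade 2, and that the assessment windows are not tied to them.

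**Increase after a reduction.** A reader might infer that Section 6.1.5 allows an increase after a toxicity reduction. The dose it refers to is the cycle 1 dose of 150, so a patient already reduced to 100 is not plainly covered.

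**The cited evidence.** A reader might infer that Section 2.4 misstates its support, because neither cited study gave 200 mg/m² with everolimus 10 mg every day. In the phase I study 200 mg/m² "was attempted only in combination with an everolimus dose of 2.5 mg/day"; in the melanoma study "patients were treated with everolimus 10 mg/d 5 days/week". But Section 2.4 reports both regimens openly, including dose reductions for myelotoxicity in 9 of 48 melanoma patients, so it contains no misstatement. Whether that experience supports the option is a clinical judgement.

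**Conclusion.** The point holds as a conflict between stated dosing rules. For an Arm 2 patient with a level 1 or 2 nadir, Table 6-7 holds the dose at 150 mg/m² while Section 6.1.5 permits 200, a difference of one third per course. The tolerance condition and the cycle at which the increase may occur also differ across Sections 2.4 and 6.1.5 and Table 6-1b.

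A reader might infer that all 35 Arm 2 patients and 11 of 12 courses are affected. That counts everyone open to physician discretion, not those for whom the rules give different doses. The documents give no expected frequency of level 1 or 2 nadirs, so the planned 35 is only a ceiling. Discretion would vary dose intensity in any case, and no effect on PFS-33 is claimed.

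The misaligned assessment windows are secondary. That part assumes an undelayed cycle 2 and counts Day 1 as the first temozolomide dose.

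**What to change.** The clinical team should reconcile Section 2.4, Section 6.1.5, Table 6-1b, Section 6.2.3 and Table 6-7 so that they state one escalation condition and one timing throughout. The text should say which passage governs when Table 6-7 leaves the dose unchanged. If the first cycle's tolerance remains the condition, its meaning should be stated where the dosing rule is given. The assessment windows in Section 7.1.2 should be reconciled with the recovery criteria in Section 6.2.3.

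What the condition, the timing and the dose should be is for the clinical team; none is proposed here. The cost is an amendment to wording in a few places. It needs no new test and leaves the sample size and the analysis as they are.
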